18. MONITORING PROCEDURES

18.1. Study Monitoring

The study will be periodically monitored and/or audited by a representative of Bellerophon Pulse Technologies LLC. It is the responsibility of the Principal Investigator or responsible designee to provide all study records, including, but not limited to, case report forms and source documentation, to the monitor and/or auditor at their visit.

Regulatory Agencies, in the person of a scientifically trained and properly authorized employee of the Agency, may request access to all study records, including source documents, for inspection and copying.

The site's Institutional Review Board/Independent Ethics Committee (IRB/IEC) may also review their individual site's study records, including, but not limited to, case report forms and source documentation at any time.

19. RESPONSIBILITIES

19.1. Quality Control and Quality Assurance

Prior to study initiation, there will be an Investigator meeting and/or individual site initiation visits to prepare Investigators and study staff, and to standardize performance at each study center associated with the study. Data will be collected by the study site coordinator and/or designee as specified on the site's "Signature Sheet and Delegation of Responsibility Log" and verified at the site by the clinical research associate (CRA). These data will be monitored and verified to the original medical records or as otherwise feasible based on current emerging guidelines provided by FDA on Conduct of Clinical Trials of Medical Products during COVID-19 Public Health Emergency. Data will be entered by trained and qualified study site personnel into a validated EDC system managed by the Sponsor. Changes to the data will be made by the research team at the site according to ICH GCP styles of recording data and will be documented via an audit trail.

19.2. Audits and Inspections

To ensure compliance with GCP and all applicable regulatory requirements, Bellerophon Pulse Technologies LLC may conduct a quality assurance audit with considerations under COVID-19 restrictions. Regulatory agencies and other governing bodies may also conduct a regulatory inspection of this study.

To ensure compliance with the protocol, GCPs, and all applicable regulatory requirements, Bellerophon Pulse Technologies LLC or an independent third party on behalf of the Sponsor, may conduct a quality assurance audit. Regulatory agencies or the local health authority may also conduct a regulatory inspection of this study. Such audits/inspections can occur at any time during or after completion of the study. If an audit or inspection occurs, the Investigator and institution agree to allow the auditor/inspector direct access to all relevant documents and allocate his/her time and the time of his/her staff to the auditor/inspector to discuss findings and/or any relevant issues. The Investigator will be informed of such audit(s).

19.3. Investigator and Study Staff Requirements

All Investigators must be qualified by training and experience to conduct the proposed research, and must accept responsibility for all research activities at their site.

Prior to study initiation, the Investigator will complete and submit to the Sponsor all documents required by 21 CFR Part 50, 56, and 312, ISO 14155, and/or ICH (E6) (Section 8.0), including financial disclosure information as required. Additionally, each Investigator must assure the study staff is qualified by training and experienced to assist with the proposed research. This training must be documented and maintained at the study site.

Upon completion or termination of the study, the Investigator will submit a final written report to the IRB/IEC. The Investigator will provide the Sponsor or designee with copies of all IRB/IEC actions regarding the study.

2.0 Change History

Version/Date	Change Log
0.6	Draft Version
1.0 / 26-OCT-2020	Final Version

4.0 Purpose

The Statistical Analysis Plan (SAP) describes the statistical methods to be used during the reporting and analyses of data collected under Bellerophon Pulse Technologies LLC Protocol PULSE-CVD19-001.

5.0 Scope

This SAP describes the statistical methods to be used during the reporting and analyses of data collected for Bellerophon Pulse Technologies LLC protocol PULSE-CVD19-001, titled "A Randomized, Double-Blind, Placebo Controlled Study to Assess the Efficacy and Safety of Pulsed, Inhaled Nitric Oxide (iNO) Versus Placebo in Subjects With Mild or Moderate Coronavirus Disease (COVID-19)".

The Statistical Analysis Plan outlines the following:

- Study Objectives
- Study Design
- Study Endpoints
- Applicable Study Definitions
- Statistical Methods

6.0 Introduction

The study protocol provides conduct for a randomized, double-blind, placebo-controlled study to assess the efficacy and safety of pulsed iNO compared to placebo in subjects with COVID-19 who are hospitalized and require supplemental oxygen without assisted ventilation. Subjects will receive placebo or iNO125 mcg/kg ideal body weight (IBW) /hr for 24 hours daily until resolution of hypoxemia, protocol defined respiratory failure, hospital discharge or Day 28, whichever occurs first. This study will be conducted with one interim analyses, when 100 subjects complete Day 28 on the protocol to assess safety and potential futility of the IP, as detailed in Section 8.0 of this SAP.

This SAP has been developed and should be read in conjunction with the study protocol and case report form (CRF) referenced on the signature page.

Changes made to the SAP after it has been approved but prior to final analyses of data will be documented in an amendment. Important changes to the SAP, along with the justification for the changes, will be described in the CSR. Changes to the protocol will require a SAP amendment ONLY if the changes are to a principal feature of the protocol.

7.0 Study Objectives

The study protocol objectives are as follows:

Primary Objective: To verify the efficacy of INOpulse in subjects with COVID-19.

Secondary Objective: To evaluate the safety of INOpulse in subjects with COVID-19.

8.0 Study Design

This is a randomized, double-blind, placebo-controlled study to assess the efficacy and safety of pulsed iNO compared to placebo in subjects with COVID-19 who are hospitalized and require supplemental oxygen without assisted ventilation. Subjects will receive placebo or iNO125 mcg/kg IBW/hr for 24 hours daily until resolution of hypoxemia, protocol defined respiratory failure, hospital discharge or Day 28, whichever occurs first. Subjects will be followed through 30 days after discontinuation of INOpulse therapy to assess their clinical status.

An unblinded independent Data Monitoring Committee (DMC) will review safety data including adverse events and adverse events of special interest. The roles and responsibilities of the DMC, including membership, scope, frequency of meetings and communication plan are defined in the current DMC charter on file with the sponsor. DMC members will evaluate the overall safety profile of INOpulse for subjects who received treatment compared to subjects who received the placebo.

There is one planned interim analyses for this study in order to assess potential futility of the INOpulse group versus placebo based on the primary endpoint of death/respiratory failure (DRF). The interim analysis will occur after the first 100 subjects complete 28 days on the protocol, and will evaluate interim safety and potential futility. The DMC will make the determination to either continue the trial, or to stop the trial due to safety concerns or futility, based on DRF. The interim analyses results will be evaluated by the DMC based on pre-specified criteria and stopping rules as detailed in this SAP. The final analysis will be conducted using the full sample size of all subjects enrolled, according to the population definitions ("Analysis Sets") described in Section 11.0 below.

8.1 Sample Size Considerations

Initial assessment of the sample size is based on the historical experience of ~30% of hospitalized COVID-19 subjects deteriorating to needing increased respiratory support and the preliminary experience in the Emergency Expanded Access that indicated ~15% of INOpulse-treated subjects deteriorate.

More recent data suggest that ~15% of hospitalized COVID-19 subjects deteriorate to needing increased respiratory support. We hypothesize that ~6% of iNO-treated subjects deteriorate.

Using 15% for the placebo arm and 6% for the INOpulse arm, a total sample size of 500 subjects yields 93% statistical power for a 1:1 randomized trial with a two-sided p-value of 0.05.

Based on this analysis of the DRF endpoint, we are targeting a sample size of 500 subjects.

8.2 Randomization and Stratification

Subjects will receive placebo or iNO125 mcg/kg IBW/hr for 24 hours daily until resolution of hypoxemia, protocol defined respiratory failure, hospital discharge or Day 28, whichever occurs first. Randomization will be stratified based on the following four [2-level] factors in Table 1 below:

Table 1: Stratification Factors

Factor	Low	High
Oxygen Use	≤5 L/min	>5 L/min
NT-proBNP	<320 pg/ml	≥320 pg/ml
# of Comorbidities	0 or 1	≥2
Remdesivir use	No	Yes

The four comorbidities considered are

1. Diabetes;
2. Hypertension;
3. Cardiovascular disease (including ischemic heart disease, heart failure, cerebrovascular disease, peripheral vascular disease);
4. Obesity (BMI ≥ 30).

9.0 Study Endpoints

Objectives	Endpoints
Primary	Primary endpoint

 The primary objective in this study is to verify the efficacy of INOpulse in subjects with COVID-19. 	
 Proportion of subjects who died or had respiratory failure (DRF as defined in Section 10.0 below) through Day 28.
	Secondary Endpoints
	
 8-point NIAID ordinal scale (Table 2 below) assessed at Day 7, 14, 28 and day of discharge. Proportion of subjects to recover, defined as return to room air or baseline oxygen requirements, or discharged alive from hospital [Through Day 28]. Proportion of subjects discharged alive from hospital [Through Day 28] Duration of hospitalization [Through Day 28]. Mortality [Through Day 28]: 
 All-cause mortality Cardiopulmonary mortality Proportion of subjects with a negative conversion of RT-PCR from a nasopharyngeal or bilateral nasal swab [through Day 28].
Secondary	
 The secondary objective in this study is to evaluate the safety of INOpulse in subjects with COVID-19.
	
 Proportion of subjects with adverse events leading to study drug discontinuation [Through Day 28].

Table 2: 8-Point NIAID Ordinal Scale

Score	Outcome
1	Death
2	Hospitalized, requiring mechanical ventilation or ECMO
3	Hospitalized, requiring non-invasive ventilation or high flow oxygen
4	Hospitalized, requiring supplemental oxygen
5	Hospitalized, not requiring supplemental oxygen - requiring ongoing medical care (COVID-19 related or otherwise)
6	Hospitalized, not requiring supplemental oxygen - not requiring ongoing medical care (COVID-19 related or otherwise)
7	Not hospitalized - limitation on activities and/or requiring home oxygen
8	Not hospitalized, no limitations on activities

10.0 Conventions and Derivations

The primary endpoint is the proportion of subjects who died or had respiratory failure (DRF) through day 28 (treatment day 27), where respiratory failure is defined as one of the following:

- Endotracheal intubation and mechanical ventilation;
- Extracorporeal membrane oxygenation;
- High-flow nasal cannula oxygen delivery (i.e., reinforced nasal cannula delivering heated, humidified oxygen with fraction of delivered oxygen ≥ 0.5 and flow rates of ≥ 30 l/min);
- Noninvasive positive pressure ventilation;
- Clinical diagnosis of respiratory failure with initiation of none of these measures only when clinical decision-making is driven solely by resource limitation or in the event the subject is not intubated due to do not intubate (DNI) or do not resuscitate (DNR) status.

Duration of therapy will be calculated as the date of first dose of study drug on the INOpulse Usage Form through the date of last dose of study drug on the End of Treatment CRF page.

Baseline is defined as the last assessment prior to the first dose of study drug.

Body Mass Index is defined as subject weight (kg) divided by height (m²).

The age at COVID-19 diagnosis is defined as the number of years from the date of birth to the date of diagnosis of COVID-19, which will be derived based on the table below. No imputation will be done for missing disease diagnosis date (Year, Month, Day). The age calculation will be truncated to a whole number.

Table 3: Calculation for Age at COVID-19 Diagnosis

Observed Portion	Missing Portion	Formula to Calculate Duration
Year, Month, Day		(Date of Diagnosis – Date of Birth + 1)/365.25
Year, Month	Day	[Year (Date of Diagnosis) – Year (Date of Birth)] + [Month (Date of Diagnosis) – Month (Date of Birth)]/12
Year	Month, Day	[Year (Date of Diagnosis) – Year (Date of Birth)]

11.0 Analysis Sets

11.1 All Randomized Analysis Set

The All Randomized Analysis Set (ARAS) includes all subjects who are randomized in the study. That is the primary analysis set for by-subject listings.

11.2 Full Safety Set

The Full Safety Set (FSS) includes all randomized subjects who received any amount of study drug. This is the primary analysis set for safety analyses.

11.3 Full Efficacy Set

The Full Efficacy Set (FES) includes all randomized, COVID-confirmed subjects who received any amount of study drug. Note that subjects who began study treatment with high suspicion of COVID infection but subsequently had negative test results on the RT-PCR swab – will be excluded from FES.

11.4 Per Protocol Analysis Set

The Per-Protocol Analysis Set (PPAS) is a subset of FES, to be used for secondary analysis of efficacy. FES subjects with at least one of the following protocol deviations will be excluded from the PPAS:

- Subject did not meet all protocol-specified inclusion criteria or met at least one of the protocol-specified exclusion criteria.
- Subject received study drug other than the one that he/she was randomized to receive
- Subjects with any other protocol deviation identified in the course of study monitoring which, in the opinion of the Sponsor's Responsible Medical Officers based on blinded review, is likely to impact the validity of the data

12.0 Interim and Final Analyses

12.1 Interim Analysis

The interim analysis for futility is planned after ~100 subjects have completed assessments through Day 28 in order to compare the failure rate in the INOpulse group versus placebo for the primary endpoint of DRF (defined in Section 10.0 above). If the observed DRF rate in the INOpulse group is ≥ 2.5 percentage points higher than that of placebo ($\pi_t - \pi_c \geq 0.025$), then the study will stop for futility (without regard to statistical significance).

12.2 Final Analysis

Final analyses outlined in this SAP will be carried out after:

- The SAP has been approved
- The study database has been locked and Bellerophon authorizes the release of the randomization assignments
- Protocol deviations have been categorized (into types of deviations), classified as important/ not important, and finalized
- Membership in the PPAS, based on blinded data and review, has been determined and finalized.

13.0 Statistical Methods

All analyses will use SAS version 9.4 or higher.

Data from all study sites will be pooled for analyses.

Unless otherwise noted, all summaries will be provided by treatment group: INOpulse and placebo. Demographic summaries will also be provided by stratification group (separately for each stratification factor, described in Section 8.2 above) as a subgroup analysis.

Unless otherwise noted, continuous variables will be summarized using number of observations (n), mean, standard deviation (std), median, first quartile (Q1), third quartile (Q3), minimum and maximum values. The minimum and maximum values will be displayed to the same level of precision as the raw data; the mean, median, Q1 and Q3 values to one additional decimal place and the std to two additional decimal places.

Categorical variables will be summarized using counts and percentages. Percentages will be rounded to one decimal place, except 100% will be displayed without any decimal places and percentages will not be displayed for zero counts.

All participants will be used in the analyses, as per the analysis populations described in Section 11.0 above, using all non-missing data available. Missing data in the logistic regression analysis of DFR will be analyzed as follows: If there is missing data for more than 5% of the cases for the outcome variable, a tipping point analysis will be performed. This will be done as a sensitivity analysis to determine whether or not the data is missing at random, and if the data is not missing at random, how robust is the parameter estimate in the model. The MI and MIANALYZE procedures in SAS¹ will be used to perform this analysis.

As a secondary sensitivity analysis, if there is missing data for more than 5% of the subjects at any time point in the NIAID assessments, the MI procedure in SAS will be utilized to impute missing values for NIAID score, and the statistical models will be run again using the imputed data points to compare the validity of the results using MIANALYZE.

1. SAS/STAT 14.2 User Guide. 2016, 6130 – 6135. SAS Institute Inc., Cary, NC.

Unless otherwise noted, values for missing laboratory and vital sign values will not be imputed. However, a missing baseline result will be replaced with a screening result, if available. If laboratory values for a subject are missing for any reason at a time point, the subject will be excluded from the calculation of summary statistics for that time point. If no pre-treatment laboratory value is available, the baseline value will be assumed to be normal (i.e., no grade [Grade 0]) for the summary of graded laboratory abnormalities.

For all tabulations of data by study time points according to a study day (e.g., Day 7, 14, 28, but not discharge or end of treatment), time windows of ± 3 days will be used to associate data with a time point, as shown in Table 4 below.

Table 4: Visit Windows

Nominal Day / Visit	Window
Day 7	Days 4 – 10
Day 14	Days 11 – 17
Day 28	Days 25 – 31

If there are multiple records within the same window, the latest one will be used for analyses.

For analyses of laboratory data that are continuous in nature but are less than the lower limit of quantitation (LLOQ) or above the upper limit of quantitation will be imputed to the value of the lower or upper limit minus or plus 1 significant digit, respectively (e.g., if the result of a continuous laboratory test is < 30, a value of 29 will be assigned; if the result of a continuous laboratory test is < 30.0, a value of 29.9 will be assigned). If the results of continuous lab test is <1, the imputed value should be 0.9; If the results of the lab test is <0.1, the imputed value should be 0.09. The actual reported values will be provided in by-subject listings.

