- Review of prior and concomitant medications, that includes all current COVID-19 treatments (all therapies prescribed for the treatment of COVID-19)

On the day of Randomization (Day 0):

- Review inclusion and exclusion eligibility criteria
- Review of prior and concomitant medications, that includes all current COVID-19 treatments (all therapies prescribed for the treatment of COVID-19)
- Electrocardiogram (ECG)
- Vital signs (heart rate, respiratory rate, blood pressure, temperature)
- Oxygen saturations
- Document oxygen flow requirements

- Upon initiating INOpulse, methemoglobin should be < 3% and SpO2 > 89% (with supplemental oxygen if required) prior to continuing with treatment. Methemoglobin will be monitored prior, during the 1st hour (every ½ hour), and approximately 4-5 hours after initiation of INOpulse therapy.
- Adverse event(s) assessment

Daily assessments while on INOpulse and hospitalized (up to Day 27) will be performed as follows:

- Review of prior and concomitant medications, that includes all current COVID-19 treatments (all therapies prescribed for the treatment of COVID-19)
- Oxygen flow requirements
- While hospitalized and on INOpulse, vital signs (heart rate, respiratory rate, blood pressure, temperature), SpO2 via pulse oximetry and methemoglobin will be measured **twice daily** to minimize exposure to healthcare professionals
 - In the event an increase in oxygen flow rate is clinically indicated, vital signs and SpO2 should be monitored every 6 hours until stabilized.
- Adverse event(s) assessment
- Respiratory Failure status
- Clinical status using an 8-point NIAID ordinal scale ([Table 1](#))

At **End of Treatment** (INOpulse discontinuation), the following assessments will be completed:

- CBC with differential, chemistry panel (sodium, potassium, chloride, CO2, BUN, creatinine, glucose), LFTs (AST/ALT and total bilirubin), triglycerides, troponin (High Sensitivity Cardiac Troponin [HS-cTN], procalcitonin, ferritin, fibrinogen, D-dimer, NT-proBNP and LDH. If available locally, CRP, Von Willebrands Factor, Factor VIII Activity, Protein C, Protein S, Homocysteine, Antithrombin 3, Thrombelastography (TEG), G6PD deficiency and Prothrombin gene G2021A
- COVID-19 RT-PCR obtained by nasopharyngeal or bilateral nasal swab
- Review of prior and concomitant medications, that includes all current COVID-19 treatments (all therapies prescribed for the treatment of COVID-19)
- Electrocardiogram (ECG)

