- Vital signs, methemoglobin and oxygen saturations
- Oxygen flow requirements
- Respiratory Failure Status
- Clinical status using an 8-point NIAID ordinal scale ([Table 1](#))
- Upon discontinuation of INOpulse, irrespective of reason, subjects should be monitored for 1 hour for symptoms of pulmonary rebound which include hypoxemia, bradycardia, tachycardia, systemic hypotension, shortness of breath, near-syncope, and syncope. SpO2, BP and vital signs should be measured every 30 minutes for 1 hour.
- Adverse event(s) assessment
- Download usage data from the INOpulse device

If a subject has completed **End of Treatment** (off INOpulse) and is **still hospitalized** (not discharged), daily assessments (up to Day 28 or day of discharge if earlier) will be performed as follows:

- Respiratory Failure status
- Clinical status using an 8-point NIAID ordinal scale ([Table 1](#))
- Adverse event(s) assessment
- Concomitant medications

At time of hospital **discharge**, if before the End of Study assessment, the following assessments will be completed:

- CT scan or chest x-ray prior to discharge, as clinically indicated
- Duration of hospitalization
- Respiratory Failure Status
- Clinical status using an 8-point NIAID ordinal scale ([Table 1](#))
- Adverse event(s) assessment
- Concomitant medications

If a subject has been discharged from the hospital, the following assessments will be completed on **Day 7, Day 14 and Day 28** via telephone:

- Respiratory Failure status
- Clinical status using an 8-point NIAID ordinal scale ([Table 1](#))
- Adverse event(s) assessment
- Concomitant medications

End of Study: Thirty (30) days following the last dose of INOpulse, subjects will be assessed for the following via telephone (or in person in the unlikely event the subject is still hospitalized):

- Respiratory Failure status
- Clinical status using an 8-point NIAID ordinal scale ([Table 1](#))
- Adverse event(s) assessment
- Concomitant medications

At **Early Discontinuation** (if applicable), the following assessments will be completed:

- CT scan or chest x-ray any time prior to discharge, as clinically indicated

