INOpulse therapy using iNO125 (125 mcg/kg IBW/hr) was authorized for treatment of COVID-19 via FDA's Intermediate Expanded Access Program in March 2020. Eligible patients were COVID-19 positive by RT-PCR, or with high suspicion of infection, and receiving supplemental oxygen at no more than 10 L/min. Data from the first 25 patients treated with INOpulse for COVID-19 was conducted in April 2020, and demonstrated INOpulse was well tolerated with no increase in methemoglobin levels above 1.5%. Of the 22 COVID-19 positive patients to complete treatment with INOpulse, 19 completed treatment without deterioration (86%) with 3 showing signs of deterioration (1 death and 2 intubated). The median time for INOpulse treatment was 4 days and the median time from start of INOpulse treatment to hospital discharge was 6 days.

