10. TABLE 2: SCHEDULE OF ASSESSMENTS

Assessments	Screening	Baseline/ Randomization	On INOpulse (Up to Day 28) (Hospitalized)		Off INOpulse (Hospitalized)	Hospital Discharge* (if prior to End of Study)	If Discharged (Phone Call)	End of Study**	Early Discontinuation***
	0 to -14 days prior to Baseline	Day 0	Daily (Up to Day 27)	End of Treatment	Daily (Up to Day 28 or Day of Discharge if Earlier)	Day of Discharge	Day 7 Day 14 Day 28 (± 2 days)	30 Day Follow Up Post INOpulse completion (± 3 days)	If Applicable
Informed consent	X								
Medical History ¹⁰	X								
Review Eligibility Criteria	X	X							
Prior & Concomitant Medications ⁹	X	X	X	X	X	X	X	X	X
RT-PCR for COVID-19 ¹	X			X					X
Chest CT Scan or x-ray ⁴	X					X			X
Pregnancy Test (urine or serum)	X								
Vital signs ²	X	X	X	X					X
Methemoglobin ³		X	X	X					X
SpO ₂ via pulse oximetry ⁷ & O ₂ flow rate	X	X	X	X					X
Electrocardiogram (ECG)		X		X					X

Assessments	Screening	Baseline/ Randomization	On INOpulse (Up to Day 28) (Hospitalized)		Off INOpulse (Hospitalized)	Hospital Discharge* (if prior to End of Study)	If Discharged (Phone Call)	End of Study**	Early Discontinuation***
	0 to -14 days prior to Baseline	Day 0	Daily (Up to Day 27)	End of Treatment	Daily (Up to Day 28 or Day of Discharge if Earlier)	Day of Discharge	Day 7 Day 14 Day 28 (± 2 days)	30 Day Follow Up Post INOpulse completion (± 3 days)	If Applicable
Lab Evaluation ⁶	X			X					X
Physical Examination	X								
Clinical status using 8-point NIAID ordinal scale			X	X	X	X	X	X	X
Respiratory Failure Status				X	X	X	X	X	X
Monitor for pulmonary rebound for 1 hr post INOpulse discontinuation ⁸				X (upon INOpulse discontinuation)					X
INOpulse Device Set up & Dose Programming ⁵		X							
Drug Dispensing ⁵		X	X						
Download of INOpulse usage data				X					X
AE and SAE		X	X	X	X	X	X	X	X

¹ RT-PCR test for COVID-19 obtained from an upper respiratory tract specimen is required within 4 days of randomization. Another sample should be obtained from the nasopharynx or bilateral nares using a swab at End of Treatment. Subjects may be positive for COVID-19 or have high suspicion of infection at the time of randomization with RT-PCR results pending. If a subject is randomized based upon a high suspicion of COVID-19 infection and the swab RT-PCR comes back negative, a repeat RT-PCR swab can be taken and the

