10.1.8. Respiratory Failure Status

Respiratory failure is defined as one of:

- Endotracheal intubation and mechanical ventilation
- Extracorporeal membrane oxygenation
- High-flow nasal cannula oxygen delivery (i.e., reinforced nasal cannula delivering heated, humidified oxygen with fraction of delivered oxygen ≥ 0.5 and flow rates of ≥ 30 l/min)
- Noninvasive positive pressure ventilation
- Clinical diagnosis of respiratory failure with initiation of none of these measures only when clinical decision-making is driven solely by resource limitation or in the event the subject is not intubated due to do not intubate (DNI) or do not resuscitate (DNR) status

10.1.9. 12-Lead Electrocardiogram (ECG)

12-Lead ECGs will be obtained and read locally after the subject has rested in a supine position for at least 5 minutes. Date, time, heart rate, and ECG interpretation will be recorded.

10.1.10. 8-point NIAID Ordinal Scale

The ordinal scale is an assessment of the subject's clinical status. The subject's clinical status should be assessed as described in **Table 2** and documented in medical records. Assessments should be performed every morning when subjects are hospitalized and via phone if discharged from the hospital as detailed in **Table 2**.

The 8-point NIAID Ordinal Scale is provided on the following page.

The scale is as follows:

Score	Outcome
1	Death
2	Hospitalized, requiring mechanical ventilation or ECMO
3	Hospitalized, requiring non-invasive ventilation or high flow oxygen
4	Hospitalized, requiring supplemental oxygen
5	Hospitalized, not requiring supplemental oxygen - requiring ongoing medical care (COVID-19 related or otherwise)
6	Hospitalized, not requiring supplemental oxygen - not requiring ongoing medical care (COVID-19 related or otherwise)
7	Not hospitalized - limitation on activities and/or requiring home oxygen
8	Not hospitalized, no limitations on activities

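### The SAP takes the latest record in each ±3-day window, so the Day 7 and Day 14 NIAID scores of subjects still in hospital can come from up to three days later

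*SAP*

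**What the plan says.** SAP Section 13.0 states that "time windows of ± 3 days will be used to associate data with a time point". Table 4 gives Days 4–10 for Day 7, Days 11–17 for Day 14 and Days 25–31 for Day 28. The selection rule follows: "If there are multiple records within the same window, the latest one will be used for analyses".

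Inpatients will routinely have several NIAID records in a window. Protocol Section 10.1.10 says: "Assessments should be performed every morning when subjects are hospitalized". The synopsis repeats this for subjects on the device ("Daily assessments while on INOpulse and hospitalized (up to Day 27) will be performed as follows") and for those off the device but still admitted ("daily assessments (up to Day 28 or day of discharge if earlier) will be performed as follows"). After discharge, Table 2 of the protocol schedules one telephone call per time point: "Day 7 Day 14 Day 28 (± 2 days").

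SAP Section 13.5.5.1 names Days 7, 14, 28 and the day of discharge as the NIAID assessment days. It gives no selection rule that would override Section 13.0. Under SAP Section 13.5.2 the secondary endpoints are tested in the order listed in Section 13.5.5, so NIAID comes first.

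**The concern.** When a score is collected every day, a score for Day 7 exists on Day 7. A latest-record rule passes over it and takes the score at the far end of the window. Subjects already at home have no such run of records, so theirs is a call close to the nominal day. The day on which a subject is measured then depends on whether that subject has been discharged, and being in or out of hospital separates scores 2–6 from 7–8 on this scale.

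What is at stake is the meaning of the by-time-point results. A subject on oxygen in hospital on Day 7 (score 4) who goes home on Day 10 can appear at Day 7 as 7 or 8. A subject alive on Day 7 whose death is recorded on Day 9 can appear at Day 7 as 1. The example model in SAP Section 13.5.5.1 contains age, baseline oxygen, comorbidities and treatment, with no term for visit or actual day. Nothing downstream corrects for the shift.

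**Working it through.** **Inputs.** The windows and the latest-record rule are from SAP Section 13.0 and Table 4. Daily inpatient scoring, up to Day 28 or discharge, is from the protocol synopsis, Table 2 and Section 10.1.10. The call within ±2 days and the End of Study contact at last dose + 30 ± 3 days are from protocol Table 2.

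**Step 1: the plan's own windows.** 7 ± 3 = 4 to 10; 14 ± 3 = 11 to 17; 28 ± 3 = 25 to 31. All three agree with Table 4.

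**Step 2: which record becomes Day 7.** Assume daily scores through the day of discharge, and a call on Day 5, 7 or 9 if the subject has already left.

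| Discharge day | Latest record in window (SAP) | Record closest to Day 7, ties to the earlier |
|---|---|---|
| 4 or earlier | the call: Day 5, 7 or 9 | the same call |
| 5 | Day 5, or call on Day 7 or 9 | Day 5 or 7 |
| 6 | Day 6, or call on Day 7 or 9 | Day 6 or 7 |
| 7 | Day 7, or call on Day 9 | Day 7 |
| 8 | Day 8, or call on Day 9 | Day 7 |
| 9 | Day 9 | Day 7 |
| 10 or later | Day 10 | Day 7 |

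Add 7 to every day and the same table holds for Day 14: a subject in hospital on Day 17 is analysed with the Day 17 score.

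The rows for discharge on Days 8 to 10 assume that a discharge-day record may fill a window. SAP Section 13.0 leaves discharge out of the windowed time points but does not say whether a discharge record can serve as Day 7.

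**Step 3: Day 28.** Daily scoring stops at Day 28, so inpatients are not shifted here. An End of Study contact falls at last dose + 27 to last dose + 33. It can lie within the window (Day 31 at the latest) if the last dose is on Day 4 or earlier (4 + 27 = 31). If made exactly on schedule, it does so only for a last dose on Day 0 or 1 (1 + 30 = 31). This is a small group, but in it the End of Study contact can displace a Day 28 call.

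**Step 4: how many records move (illustration).** Protocol Section 5 reports for expanded access that "the median time from start of INOpulse treatment to hospital discharge was 6 days". Assume exponential discharge times with median m, so the proportion still in hospital is S(t) = 0.5^(t/m), ignoring deaths.

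- m = 6: S(7) = 44.5%, S(10) = 31.5%, S(14) = 19.8%, S(17) = 14.0%.
- Leaving between Days 7 and 10: 44.5 − 31.5 = 13.0% of all subjects. Between Days 14 and 17: 19.8 − 14.0 = 5.8%.
- Range over m = 4 to 9 days: S(10) = 17.7% to 46.3%; S(17) = 5.3% to 27.0%.

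These figures count records taken later. They do not measure bias: a score of 4 on Day 7 may still be 4 on Day 10.

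**Step 5: does the shift favour one arm?** The same model, with assumed medians, gives the between-arm gap in the percentage still in hospital:

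| Assumed medians, iNO v placebo | Day 7 | Day 10 | Day 14 | Day 17 |
|---|---|---|---|---|
| 6 v 9 days | 58.3 − 44.5 = 13.8 | 46.3 − 31.5 = 14.8 | 34.0 − 19.8 = 14.2 | 27.0 − 14.0 = 13.0 |
| 4 v 6 days | 44.5 − 29.7 = 14.8 | 31.5 − 17.7 = 13.8 | – | – |

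The gap widens by 1.0 point in one case and narrows by about 1 point in the others. The sign depends on inputs that the documents do not give.

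**The case against.** The strongest reply is that little rides on this. The rule is the same in both arms and creates no difference when there is none. The primary endpoint is cumulative through Day 28 and does not use these windows for its definition. NIAID is tested only if the primary endpoint succeeds, and the model in SAP Section 13.5.5.1 estimates one treatment coefficient pooled over assessments, not a Day 7 contrast. Section 13.0 also introduces the windows for tabulations before it speaks of analyses, so their use in the model is not explicit. All of this stands and limits the point to the meaning of a secondary endpoint and its tables.

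A reader might go further in four ways that the documents do not support.

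- **That the rule shrinks a true benefit by giving the slower arm extra recovery time.** Step 5 shows the shift can go either way. Later scores also pick up deaths and intubations on Days 8 to 10, which could widen a true difference. The 6-day median comes from a small, uncontrolled, iNO-treated series and says nothing about placebo.
- **That it endangers the rest of the testing hierarchy.** Without a known direction or size, no loss of power for NIAID, and so none for later endpoints, can be claimed.
- **That every inpatient's Day 7 score is a Day 10 score.** This is exact only for those still in hospital on Day 10.
- **That ±3 days in the SAP contradicts ±2 days in the protocol.** One is an analysis window and the other a scheduling tolerance for calls. Narrowing to ±2 could drop usable records.

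None of these replies explains why a Day 7 score should be set aside for a Day 10 score when both exist.

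**Conclusion.** The point holds as a labelling and definition fault. Read as written, SAP Section 13.0 discards the actual Day 7 or Day 14 NIAID score of any subject still in hospital on Day 10 or 17. It may represent subjects discharged on Days 8 to 10 by a discharge-day or later record, while subjects already at home are scored near the nominal day. The results labelled Day 7 and Day 14 therefore do not describe status on those days.

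The shift is up to three days. Under the assumed exponential model with a 6-day median, the full three-day shift applies to 31.5% of subjects at Day 7 and 14.0% at Day 14, with wide ranges for other medians. The direction and size of any effect on the treatment comparison cannot be determined from the documents. Type I error and the primary endpoint are unaffected.

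The conclusion assumes that the window rule applies to NIAID, which Section 13.0 implies by naming Days 7, 14 and 28. SAP Section 13.3.1 calls the first dose Day 0 while Section 13.5.5.4 calls the start of treatment Day 1. That could move the labels by a day but does not remove the gap.

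**What to change.** In SAP Section 13.0, replace the latest-record sentence with: *Use the record on the nominal day; if none, the record closest to the nominal day within the window; if two are equally close, the earlier.* Add that an End of Study call does not replace an existing Day 28 record. Keep the ±3-day window.

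In the same edit, state whether a discharge-day record may fill a Day 7, 14 or 28 window, and whether the windows govern the repeated-measures model as well as the tables. Also state how a death enters later time points. Section 13.5.5.1 is silent, and under the closest-record rule a death on Days 8 to 10 would no longer appear at Day 7, so it needs a defined place at Day 14 and Day 28.

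The cost is a few SAP sentences and a change to the visit-mapping program. No new data are needed, because the nominal-day inpatient scores are already collected.
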